10.2 Primary efficacy endpoint

The primary endpoint is PFS, which is calculated as the time period from the date of treatment start to the date of disease progression or to the date of death, whichever occurs first, or to the last follow-up date if patients are alive without disease progression. It is expected that the median PFS time will be 3 months or more under this study treatment. If the trial continues to accrual of 60 patients and maintains sufficient follow-up to observe 35 events (PD/death) with a median PFS of 3 months, then the 95% credible interval for the median PFS would extend from 2.1 to 4.2 months.

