Ramucirumab is a fully human IgG1 monoclonal antibody that is a specific and direct inhibitor of VEGFR-2, where it binds to the extracellular VEGF-binding domain with high degree of specificity and affinity, at picomolar dose range. It thus prevents the binding of the VEGF ligand to the VEGF-R2 receptor. In the phase I trial for patients with advanced solid tumors, ($n=37$) ramucirumab demonstrated encouraging early evidence of efficacy at a range of dose levels including the one enrolled patient with biliary cancer who experienced stable disease lasting over 5 months³⁰. Ramucirumab was recently shown to improve survival compared with placebo in advanced gastric cancer, with a median overall survival of 5.2 months in the ramucirumab arm, and 3.8 months in the placebo arm. The main toxicity seen was an increase in hypertension in the ramucirumab group³¹. Additionally, a double-blind, randomized, phase III study of previously treated gastric and gastroesophageal junction cancers included 665 patients randomized to ramucirumab plus paclitaxel versus placebo plus paclitaxel³². In this study, the combination arm showed an improvement in overall survival (9.6 months vs. 7.4 mths, $p=0.017$), providing further rationale for the use of ramucirumab in refractory gastric cancer.

Initial data with ramucirumab in biliary cancer

In the initial 43 patient cohort that was enrolled in this phase II trial, 42 patients with cholangiocarcinoma and gallbladder cancers received treatment. Ramucirumab was well tolerated with 9 grade 3 toxicities including anorexia, dehydration, hypertension, hyponatremia, proteinuria and vomiting. There were no grade 4 toxicities. The median PFS for all patients who received treatment was 2.73 months (95% CI 1.91-8.03 months) and median OS was 6.31 months (95% CI 4.7 months – not reached). The overall response rate was 0% and disease control rate (SD + PR + CR) was 44%. Importantly, 6 patients (13%) were on treatment for > 24 weeks. Of these, 3 were on treatment for at least 44 weeks. In reviewing the genomic data on the 6 patients with prolonged periods of stable disease, we noted that 4 of the 6 harbored mutations in DNA repair pathways (BRCA, FANCA, ARID1A) and 1 patient had an FGFR alteration

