Diagnostic Imaging for Tumor Assessment, preferably dual-energy CT ⁷	X	Every 4 cycles ⁵	X ⁶	X ⁶
Survival				X ⁹

1. Informed consent must be obtained before any evaluations are initiated. Diagnostic imaging studies must be completed within 28 days prior to first day of study treatment. All other baseline evaluations, except for height (which can be obtained at

any time prior to enrollment), must be completed within 7 days prior to first dose of study drug.

2. When patients are enrolled, we will collect their pre-existing tissue biopsies, if available, for testing. The Oligo GEArray® Human Angiogenesis Microarray profiles the expression of 113 genes involved in modulating the biological processes of angiogenesis and will be investigated for correlation with outcome, include PFS. Archival tumor biopsy specimens will be used. This investigation will be performed at MD Anderson Core Facility.
3. For Cycle 1, baseline evaluations will suffice as they are performed within 7 days prior to first dose of study drug (except for imaging studies which are performed within 28 days prior).
4. Within 72 hours prior to start of the cycle (except for Cycle 1 as noted above).
5. Imaging should be obtained every 4 cycles (+/- 1week). Evaluations earlier than every 4 cycles are allowed if, in the investigator's opinion, this evaluation is in the patient's best interest.
6. The end of treatment imaging does not have to be repeated if recent imaging has been completed within 4 weeks. For patients discontinued from the study for reasons other than progression, it is recommend to perform every 12 weeks (+/- 5 week) after the End of Treatment Evaluation visit until documentation of progression or for 12 months after their first dose of study drug, whichever comes first, if no other anti-cancer treatment is given.
7. CT of the chest, abdomen, and pelvis. MRI may be used in cases where it is felt to be unsafe to perform CT secondary to patient's history of dye allergy, or if the tumor is not adequately seen on CT for the purposes of this study.
8. Treatment-related adverse events occurring during study treatment or within 30 days (window of 28-35 days allowed) after the last administration of study drug(s) will be followed until resolution or stabilization. If the patient is unable or unwilling to return to M. D. Anderson for this assessment, the patient will be contacted by phone for this assessment.
9. Every 3 months (+/- 5 weeks) from Post-Treatment Evaluation.

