7.2 Follow-up (off-treatment)

Follow-up/observation for all treatment related adverse events will be through Day 30 (Day 28 to Day 45 allowed) following the last dose of study drug or until resolution or stabilization of the toxicity or start of another treatment regimen. If it is not feasible for the patient to return to M. D. Anderson for the Day 30 toxicity assessment, the patient will be contacted by phone for this assessment.

Patients with documented (radiological) disease progression at any point during the study will discontinue treatment with study drugs under this protocol. Objective evidence of progressive disease will be recorded at the time of progression. Patients without evidence of progression while on study, regardless of the number of treatment cycles received, will be followed for progression until it is documented. If a patient is off treatment with no documented disease progression and no subsequent anti-cancer treatment is received, he/she should be followed every 12 weeks (+/- 5 weeks) after the End of Treatment Evaluation visit with tumor evaluations until disease progression is documented or for 12 months after their first dose of study drug, whichever comes first.

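### Section 10.2 censors PFS at a last follow-up date not tied to any tumour assessment; read literally, this can raise the Bayesian median PFS slightly

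*Combined protocol and SAP*

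**What the plan says.** Section 10.2 measures PFS from treatment start to progression or death, "or to the last follow-up date if patients are alive without disease progression". That date is not defined anywhere. Sections 10.3, 10.5 and 10.6 add no censoring rule; 10.5 asks only that follow-up times be kept current.

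Two streams of follow-up could supply the date:

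- **Tumour imaging.** On treatment it is every 4 cycles of 14 days, that is 8 weeks (Section 6, Table 7). For a patient off treatment without progression or further anti-cancer therapy, Section 7.2 says "he/she should be followed every 12 weeks (+/- 5 weeks) after the End of Treatment Evaluation visit" with tumour evaluations "until disease progression is documented or for 12 months after their first dose of study drug, whichever comes first". Footnote 6 of Table 7 carries the same condition: "if no other anti-cancer treatment is given".
- **Survival contact.** Section 7.3 sets this at about every 3 months, from the medical record or by telephone, with no stated end.

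Section 7.2 also says that patients without progression "will be followed for progression until it is documented", but its next sentence sets the limits above. Section 6 retains patients interrupted for consolidative therapy for the survival analyses and does not say how their PFS is handled.

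The estimator in Section 10.6 is a Bayesian posterior estimate of the median with a 95% credible interval; Kaplan-Meier curves are also planned. For precision, Section 10.2 supposes 60 patients and enough follow-up to "observe 35 events (PD/death) with a median PFS of 3 months", and gives 2.1 to 4.2 months.

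**The concern.** A chart check or telephone call can show that a patient is alive. It does not show that the tumour has not progressed. A patient who leaves imaging without progression and is later found alive has a last follow-up date beyond the last scan, and under the literal wording the gap counts as progression-free time.

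This is the primary endpoint of a single-arm trial, and Section 10.3 sets it against a historical median of about 3 months. An exponential model uses total event-free time, so a few long gaps enter the estimate directly. Two analysts could also choose different dates and obtain different primary results from the same data.

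**Working it through.** **Model.** I take the Section 10.3 model as the final estimator, which is an assumption. With prior IG(2.5625, 4.6875) on the median, d events and T patient-months, the posterior is IG(2.5625 + d, 4.6875 + ln2 × T). The prior intervals in 10.3 come back as 2.32 to 3.88 and 0.72 to 10.66 (stated: 10.67), which supports this form.

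**The plan's own figure.** With d = 35 and median 3, T = 35 × 3 / ln2 = 151.5. The posterior is IG(37.5625, 109.6875), with mean 109.6875 / 36.5625 = 3.00 and interval 2.17 to 4.14. A log-normal approximation, 3 × exp(±1.96/√35), gives 2.15 to 4.18. Both are close to the stated 2.1 to 4.2.

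**Per credited month.** An unassessed month adds ln2 to the scale and no event, so the posterior mean rises by ln2 / 36.5625 = 0.019 month. For illustration, three patients with 3, 6 or 12 unassessed months each add 9, 18 or 36 patient-months, giving 3.17, 3.34 or 3.68.

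**Allowing for later deaths.** Deaths found by survival contact count as events and offset part of the gain, so I rely on simulation. Assumptions:
- exponential PFS with true median 3 months; leaving imaging is independent of progression;
- survival after progression has median 6.31 − 2.73 = 3.58 months (a difference of the Section 2.1 medians);
- follow-up is 6 to 36 months; scans are 8-weekly on treatment and, for leavers who are rescanned, 12-weekly to month 12;
- progression is seen without delay on treatment;
- death is an event under both rules.

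Posterior mean, last contact v last scan:

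| Leaving imaging before progression | Half of leavers rescanned | None rescanned |
|---|---|---|
| 5% | 3.10 v 3.05 | 3.15 v 3.06 |
| 10% | 3.21 v 3.11 | 3.30 v 3.15 |
| 20% | 3.42 v 3.25 | 3.61 v 3.33 |

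With no leavers the values are 3.00 v 2.98. The differences due to the rule are 0.05/0.10/0.17 and 0.09/0.15/0.28. A repeat run gave 0.06/0.09/0.17 and 0.08/0.13/0.25. If progression is dated at scans, all levels rise by about 0.5 to 0.6, with differences of 0.06/0.10/0.17 and 0.09/0.15/0.28. The Kaplan-Meier median differs by 0.01/0.02/0.04 and 0.01/0.04/0.09.

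**Longer survival after progression.** A second simulation used accrual of 2.5 per month, 6 months of further follow-up, scan-dated progression and a monthly hazard of stopping imaging. Against a progression hazard of ln2/3 = 0.231, hazards of 0.02 and 0.05 mean that about 0.02/0.251 = 8% and 0.05/0.281 = 18% leave first. Posterior medians were 3.77 v 3.60 and 4.00 v 3.68 with a post-progression median of 3.6 months, and 4.02 v 3.66 and 4.59 v 3.80 with 9 months. Nine months is well above the 3.58 that Section 2.1 suggests.

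**Reversal.** If leavers die with a median of 3 months, as fast as others progress, and none is rescanned, last contact gives 3.00/3.00/2.99 and last scan 2.97/2.95/2.92.

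**The case against.** The best reply is that being alive without progression already implies an assessment. Section 9 defines progression by RECIST, so the date could mean the last date known to be progression-free. That reading is possible and may be what was meant, but no section states it. Equally, a reader might infer that the plan directs survival calls to set the PFS date. The documents do not say that either: the term is undefined, and the upward shift follows only from the literal reading.

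Exposure is also limited, and this stands. Treatment and scans run to progression, an end-of-treatment scan is required unless a recent one exists, and 12-weekly scans follow to 12 months. Sections 9.9 and 9.10 ask for every effort to document later progression. At a 3-month exponential median, 0.5^(12/3) = 6.25% of patients, about 4 of 60, reach 12 months progression-free. Under the assumed rates, only about 0.6 to 2.6 leavers per 60 end censored.

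Three stronger readings are not supported:

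- **That 60 − 35 = 25 patients are exposed.** This is the precision scenario of Section 10.2. With all patients followed 6 months past accrual, only about 2 to 3 remain event-free.
- **That the long-treated patients in Section 2.1 prove the bias.** Of six treated beyond 24 weeks, it says: "Of these, 3 were on treatment for at least 44 weeks". If one stopped without progression at week 44, the first 12-weekly scan would fall at week 56 (week 51 at the early edge of the window), against an imaging limit of about week 52. The documents do not say whether or why these patients stopped, so this is illustration only.
- **That a decision would change.** Section 10 sets no success threshold. Section 2.1 already reports results "In the initial 43 patient cohort that was enrolled in this phase II trial", so any futility effect is confined to the remaining patients. Simulated for patients 44 to 53 (true median 2.73, half of leavers rescanned, 10 or 20% leaving), stopping credit when a patient leaves imaging moved the stopping probability by only 0.013 to 0.018.

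**Conclusion.** The point holds as a minor one. The censoring date for the primary endpoint is not tied to a tumour assessment, and survival contact outlasts planned imaging. Read literally, the rule raises the posterior mean by about 0.05 to 0.3 month if 5 to 20% of patients leave imaging before progression, and by more if they survive longer after progression. The stated interval is 4.2 − 2.1 = 2.1 months wide, and the Kaplan-Meier median moves by less than 0.1 month.

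These sizes rest on the inverse-gamma model being the final estimator and on assumed leaving rates; the number of exposed patients is not in the documents. The direction is an average, and the bias disappears if leavers die as fast as others progress.

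Last-scan censoring does not remove all of the excess. At 10% leaving with half rescanned, each rule against its own no-leaver value, it falls from 3.21 − 3.00 = 0.21 to 3.11 − 2.98 = 0.13. The rest comes from deaths dated after unseen progression, which Section 10.2 rightly counts as events.

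**What to change.** In Section 10.2, replace the clause "or to the last follow-up date if patients are alive without disease progression" with: *or, for patients alive without documented progression, to the date of the last adequate tumour assessment (treatment start if there is none after baseline)*. Keep death as an event. State what counts as adequate, for example an assessment with an overall response other than inevaluable in Section 9.9. Report last-contact censoring as a sensitivity analysis.

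Censoring at the start of new or consolidative therapy is a separate estimand choice that assumes such therapy is unrelated to prognosis. It should at most be a further sensitivity analysis.

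Leave the futility rule as it is. With last-scan dates there, no leavers and progression seen without delay, simulated stopping rises from 0.18 to 0.31 at a true median of 3 months and from 0.03 to 0.07 at 4.5. Table 11 gives 0.1674 and 0.0216 and would no longer describe the rule.

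The cost is one clause, one definition and one extra analysis, with no new data. The downside is up to one scan interval of follow-up lost per censored patient (about 3.00 to 2.98 with no leavers) and a slightly less favourable median.

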10.3 Futility monitoring

For futility monitoring, we will monitor PFS using the methods of Thall et al and we will stop enrolling patients to the study if the median PFS is not likely to be longer than that from the historical data, which is around 3 months. Specifically, the trial will be stopped if $Pr(\lambda(E) > \lambda(S) | \text{data from the trial}) < 0.05$, where $\lambda(S)$ is the median PFS for historical patients under conventional care with an inverse gamma distribution $IG(58.25, 171.75)$, which corresponds to a mean of 3 months and a standard deviation of 0.4 month (variance = 0.16), the corresponding 95% CI of (2.32, 3.88) months. The prior for $\lambda(E)$ is assumed to be $IG(2.5625, 4.6875)$, corresponding to a mean of 3 months and a larger standard deviation of 4 (variance=16, the corresponding 95% CI is 0.72-10.67). Futility monitoring will start once 5 patients have been enrolled. Assuming an accrual rate of 2 per month and an additional follow-up of 6 months, the operating characteristics for the futility stopping rule under various scenarios are summarized in Table 11 below, with results based on 5000 simulations.

Table 11: Operating characteristics for futility monitoring

Median PFS (M)	Prob(Stop Early)	Mean No. of Patients (25%, 75%)
6	0.0058	49.5 (50, 50)
4.5	0.0216	49.1 (50, 50)
3	0.1674	44.2 (50, 50)
2	0.855	23.7 (10,37)
1.5	0.9992	12.3 (7, 16)

10.4 Toxicity monitoring

Unacceptable toxicities will also be monitored closely for the study drug using the method of Thall et al (1995). Denote the probability of unacceptable toxicity by T_E , Unacceptable toxicity will be defined as follows, using the National Cancer Institute’s (NCI) Common Terminology Criteria for Adverse Events (CTCAE) v 4.0. For the purpose of toxicity monitoring, only unacceptable toxicities that occur in the first 28 days (i.e., 2 cycles) will be counted when assessing the stopping boundary. That is, a patient will be classified as not having toxicity if the patient has been treated for 28 days and no unacceptable toxicity has been observed.

- Grade 4 neutropenia lasting ≥ 5 days or Grade 3 or 4 neutropenia with fever and/or infection

- Grade 4 thrombocytopenia (or Grade 3 with bleeding)
- Grade 4 anemia
- Grade 3 or 4 non-hematological toxicity [excluding electrolyte abnormalities, alopecia or grade 3 nausea that is correctable with usual supportive medications]
- Dosing delay greater than 14 days due to treatment-emergent AEs or related severe laboratory abnormalities
- Grade 3 hypersensitivity reaction with premedication (Grade 3 hypersensitivity reaction without premedication is not considered a DLT)
- Grade 4 hypersensitivity reaction with or without premedication
- Drug-related fever \leq Grade 3 will not be considered a DLT.

We assume $T_E \sim \text{beta}(0.3, 0.7)$. We will stop the enrollment if at any point $\Pr(P_E > 0.30 \mid \text{data}) > 0.9$. That is, we will stop the trial if, at any time during the study, we determine that there is more than 90% chance that the unacceptable toxicity rate is more than 30%. This toxicity monitoring rule will be applied after the first 5 patients have been enrolled and evaluated, and then in cohort size of 5. The corresponding stopping boundaries are to stop the trial if (number of patients with unacceptable toxicities / number of patients) $\geq 4/5, 6/10, 8/15, 9/20, 11/25, 13/30, 15/35, 16/40, 18/45$. The operating characteristics (OCs) are listed in Table 12.

Table 12: OCs for unacceptable toxicity monitoring

True Prob(unacceptable tox)	Pr(stop)	mean # Pts (25%, 50%, 75%)
0.1	0.0006	49.97 (50, 50, 50)
0.2	0.0225	49.21 (50, 50, 50)
0.3	0.2215	43.59 (50, 50, 50)
0.4	0.6869	30.12 (15, 25, 50)
0.5	0.9597	17.77 (10, 15, 20)

Multc Lean V2.1 and OneArmTTE Version 4.1.1 were used for the trial design.

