The RAINBOW trial randomized 665 advanced, refractory gastric or GE junction patients to receive paclitaxel plus ramucirumab versus paclitaxel plus placebo. The addition of ramucirumab to paclitaxel significantly improved median PFS from 2.9 months to 4.4 months. Objective response rate was similarly improved from 16% to 28%. Further, the combination of paclitaxel with ramucirumab resulted in a significant improvement in overall survival from 7.4 months to 9.6 months³².

6. Potential Risks of Ramucirumab Toxicities

The most common toxicities reported with Ramucirumab as monotherapy include hypertension (16%), diarrhea (14%), headache (9%), and hyponatremia (6%). Class-related effects such as hemorrhage (3.4%), arterial thromboembolic events (1.7%), and gastrointestinal perforations (0.7%) were rarely noted. Infusion-related reactions were initially seen in 16% of patients prior to the institution of premedication recommendations.

7. Further Information and Storage

See Appendix 2 for Package Insert and Investigator's Brochure

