Dose modification or delay may occur in the setting of lower Grade toxicity if the treating physician believes that it is in the interest of a subject’s safety. Alopecia and nausea and/or vomiting that can be controlled by antiemetics do not require dose modification or interruption. No dose reduction or interruption will be required for anemia as it can be satisfactorily managed by transfusions. Dose reductions for non-hematologic toxicity should be as below.

Table 5: Dose Modifications for Ramucirumab on Day 1 of Each Cycle (Non-Hematologic Toxicity)*

Toxicity/Dose Held	Ramucirumab dose this cycle
Grade 0-2 toxicity	Same as Day 1 previous cycle
Grade 3 toxicity	Decrease ramucirumab to next lower dose level
Grade 4 toxicity	Off protocol treatment
Dose held in 2 previous consecutive cycles	Decrease ramucirumab to next lower dose level and continue throughout the rest of treatment

* Drug-specific toxicities are explained in greater detail below with appropriate modifications

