6.6 Proteinuria

If, while on therapy, a patient has proteinuria $\geq 2+$ per a dipstick (equivalent to $\geq 100-300$ mg/dl) or routine urinalysis, ramucirumab therapy will continue as scheduled, and a 24-hour urine collection will be conducted prior to the subsequent scheduled treatment cycle. If the protein level is $< 2\text{g}/24$ hours, the patient will continue on study therapy at the same dose without interruption. If the protein level is 2 to 3 g/24 hours, study therapy for the subsequent cycle will be held for up to 2 weeks and a 24-hour urine collection will be repeated. Treatment will resume at a reduced dose level (6 mg/kg every other week) once the protein level returns to $< 2\text{g}/24$ hours. A second dose reduction (to 5 mg/kg every other week) is permitted if the protein level $> 2\text{g}/24$ hours recurs. The patient will be discontinued from the study if the protein level is $> 3\text{g}/24$ hours, if there is a third occurrence of proteinuria $> 2\text{g}/24$ hours, or if the protein level does not return to $< 2\text{g}/24$ hours within 2 weeks.

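### Section 10.4 can omit from the toxicity stopping count two kinds of event that the protocol treats as serious: Grade 4 electrolyte abnormalities and long dosing delays

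*Combined protocol and SAP*

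**What the plan says.** **Counting rule (Section 10.4).** Enrollment stops if the posterior probability that the unacceptable-toxicity rate exceeds 30% is above 0.90. The prior is beta(0.3, 0.7), and looks are taken after every 5 patients. The window is explicit: "only unacceptable toxicities that occur in the first 28 days (i.e., 2 cycles) will be counted when assessing the stopping boundary".

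**What counts (Section 10.4).** The non-hematologic item is "Grade 3 or 4 non-hematological toxicity [excluding electrolyte abnormalities, alopecia or grade 3 nausea that is correctable with usual supportive medications". A separate item counts a dosing delay of more than 14 days caused by treatment-emergent adverse events or related severe laboratory abnormalities.

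**What ends treatment (Section 6, Table 5).** For Grade 4 non-hematologic toxicity the entry is "Off protocol treatment". A footnote to the table refers to drug-specific rules further on, but Sections 6.2 to 6.7 contain none for electrolytes.

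**Schedule (Section 6).** Cycles last 14 days with a dose on Day 1. Delays for toxicity are allowed up to 3 weeks in one place and up to 30 days in another, so a delay beyond 14 days can occur without ending treatment.

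**Experience so far.** Section 3.1 lists hyponatremia among the common toxicities of ramucirumab monotherapy, at 6% with no grade given. Section 2.1 reports, for the 42 patients treated in the initial cohort, "9 grade 3 toxicities including anorexia, dehydration, hypertension, hyponatremia, proteinuria and vomiting", and no Grade 4 toxicity.

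**The concern.** A stopping boundary is only as good as its numerator. Two people applying Section 10.4 should classify the same patient in the same way, and an event serious enough to end protocol treatment within 28 days should not fall outside the count by accident of wording.

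Both conditions can fail here. In the bracketed exclusion, the grade limit and the correctability condition may apply to nausea alone, which leaves electrolyte abnormalities excluded at every grade. Hyponatremia is a known toxicity of the drug, so the case is not hypothetical in kind. Separately, the delay criterion looks like a safeguard for adverse events and severe laboratory abnormalities that no other item captures, but its timing puts it out of reach of the window.

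At stake is whether the stopping probabilities in Table 12 describe the toxicity that the protocol itself regards as unacceptable.

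**Working it through.** **1. Reproduce the plan's rule.** Inputs from Section 10.4: prior beta(0.3, 0.7), limit 0.30, threshold 0.90, looks at n = 5, 10, …, 45, and a maximum of 50 patients as in Table 12. The boundary at n is the smallest x with

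Pr(p > 0.30 | Beta(0.3 + x, 0.7 + n − x)) > 0.90.

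| n | x just below boundary | boundary x |
|---|---|---|
| 5 | 3: 0.8939 | 4: 0.9839 |
| 10 | 5: 0.8901 | 6: 0.9686 |
| 40 | 15: 0.8335 | 16: 0.9029 |
| 45 | 17: 0.8580 | 18: 0.9166 |

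All nine printed boundaries match. An exact binomial recursion over the looks gives Pr(stop) of 0.0006, 0.0225, 0.2215, 0.6869 and 0.9597 at true rates of 0.1 to 0.5, which are the Table 12 values.

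**2. Electrolyte wording beside Table 5.**

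| Event in the first 28 days | Table 5 | Section 10.4 count |
|---|---|---|
| Grade 4 non-electrolyte, non-hematologic | ends protocol treatment | counted |
| Grade 4 electrolyte, qualifiers apply to nausea only | ends protocol treatment | excluded |
| Grade 4 electrolyte, grade limit applies to the whole list | ends protocol treatment | counted |
| Grade 4 electrolyte, only correctability applies to the whole list | ends protocol treatment | depends on whether it was correctable |

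The same patient is handled differently under three grammatical readings.

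**3. Delay criterion beside the window.** Cycle 1 starts on Day 1, so Cycle 2 is due on Day 1 + 14 = Day 15. A delay of that dose exceeds 14 days only after Day 15 + 14 = Day 29. The window closes on Day 28. Cycle 3 is due on Day 29, so a delay to it also falls outside.

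**4. Size, as a scenario.** No document gives the rate of Grade 4 electrolyte events. Assume a true 28-day rate of 40%, of which e points are uncounted:

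| e (assumed) | counted rate | Pr(stop) |
|---|---|---|
| 0 | 40% | 0.687 |
| 3 points | 37% | 0.544 |
| 5 points | 35% | 0.444 |

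**5. What the first 42 patients say.** With no Grade 4 toxicity in 42, the one-sided 95% upper bound on any Grade 4 rate is 1 − 0.05^(1/42) = 6.9%. If all 9 Grade 3 toxicities were in different patients and all fell inside the window, the rate would be 9/42 = 21.4% and Pr(p > 0.30) = 0.097, far below 0.90. At the last printed look, even events in all three further patients would give 9 + 3 = 12 of 45, against a boundary of 18. This tally covers graded toxicity only. Section 2.1 does not report dosing delays, and six more patients with a delay alone (18 − 12) would be needed to reach the boundary.

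**The case against.** **The sentence can be read sensibly.** A reader may apply the grade limit and correctability to the whole list, so that Grade 4 events count. That is possible, but the text does not settle it, and the ambiguity itself is the defect.

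**A patient taken off early is not literally scored as free of toxicity.** Section 10.4 gives that label to patients who have been treated for 28 days. This is correct as far as it goes. It leaves a patient removed earlier for an excluded event without any classification, and still absent from the numerator.

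**The delay item is a backstop for severe laboratory abnormalities.** It would be, if it could be met within the window. A reader might also take the gloss of two cycles to stretch the window when Cycle 2 is late, but the text equates two cycles with 28 days and does not say so.

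**The data are reassuring.** This stands. With no Grade 4 events in 42 patients, and graded toxicity well below the boundary, neither edit is likely to change a decision.

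**A stronger reading to avoid.** A reader might infer that every toxicity after Day 28 is wrongly ignored, so that a drug above the 30% limit passes unseen. The documents do not support this. Section 6 ends treatment only for listed events. The 30% limit is set on the 28-day endpoint, and a fixed window is a disclosed and legitimate choice. Later events are still collected, reported and acted on for the individual patient. Even with every event counted, a drug with a 40% rate completes with probability 1 − 0.687 = 0.313.

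**Conclusion.** The concern holds as a conflict of definitions and is minor. The electrolyte exclusion in Section 10.4 can leave out an event that Table 5 treats as ending protocol treatment, and the delay criterion cannot be met inside the window that governs it. The boundaries and Table 12 are arithmetically correct for the endpoint as counted.

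The fall in stopping probability from 0.69 to between 0.54 and 0.44 rests on two assumptions that the documents do not supply: a true 28-day rate of 40%, and 3 to 5 points of it from Grade 4 electrolyte events. The 6% hyponatremia figure carries no grade and cannot support that split. Given the first 42 patients, the effect on the remaining enrollment is small. The reason to act is that the count should be unambiguous while enrollment can continue, and that the edit is cheap.

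**What to change.** Edit the definition in Section 10.4 in two places.

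1. Reconcile the electrolyte exclusion with Table 5, stating which grades and conditions it covers, so that an electrolyte event that ends protocol treatment under Table 5 within the window is not scored as no toxicity. This concerns the count only; which patient-level rule applies is for the investigator and the sponsor to settle.
2. State that a toxicity-related delay of the Cycle 2 dose is attributed to the 28-day window even though its length is confirmed later, and that the patient's classification waits until then.

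Keep the 28-day window, the 30% limit and the boundaries.

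Do not add a cumulative trigger that reuses the 30% calculation over the full course. Follow-up would be unequal at each look, and the limit was set for a different endpoint. For illustration, assume constant hazards, a median PFS of 3 months, treatment to progression, and 28 days = 0.92 month. A 28-day risk of 10% or 15% gives a toxicity hazard of −ln(0.90)/0.92 = 0.115 or −ln(0.85)/0.92 = 0.177 per month, against a progression hazard of ln2/3 = 0.231. The full-course risks are 0.115/0.346 = 33% and 0.177/0.408 = 43%, and such a trigger would fire with probability about 0.35 and 0.82.

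The cost is a short wording change, a later classification for patients whose Cycle 2 is delayed, and a slightly higher chance of stopping under a tolerable drug. For example, if the counted rate rose from 20% to 21%, Pr(stop) would go from 0.023 to 0.030.
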